# Pharmaceutical Interventions for Noise-Induced Hearing Loss-Acute Exposure Treatment (PINIHL-AET)

## **Protocol Revision History**

Version Date	Revision Summary
19 January 2021	Initial Version
19 February 2021	
 
Clarification of baseline and follow-up blood draws that include an electrolyte panel, BUN, Cr, ALT, and AST; serum pregnancy at baseline
 
Addition of effective birth control instruction
 

10 June 2021	
 
Addition of NIOSH red flag guideline         
 
(an increase in hearing threshold level of 15 dB or more at any frequency (2, 3, 4, 6 kHz) in either ear for permanent threshold shift as a secondary endpoint
 
 
 
Addition of LENS-Q Adapted for Surgical Noise Study and stratification language
 
Surgery drilling time reduced to 45 minutes for inclusion criteria
 
Change in sample size
 
Corrected section 5.5 Follow-up Assessments to include "Hearing History and Occupation Exposure" questionnaire as listed in study calendar and appendix E
 
Study calendar clarifications including baseline testing adjusted from 1 week to 1-2 weeks
 
Numbering correction in "Hearing History and Occupation Exposure—Visit 1" questionnaire
 
Edited inclusion criteria for DPOAE as the number of data points (denominator) was incorrect
 

	Removed urine sample; Added blood sample for PGx collection at baseline visit.

	
 
Range of 2-8 degree Celsius (C) refrigerator at WUSM replaces 4 degree C for blood sample
 
Removed PI and Sub-Investigator information
 
List protocol version as a separate line.
 
Statistical considerations section updated to match SAP
 

21 October 2021	
 
Inclusion of stratification table for noise exposure
 
Randomization language updated
 

09 November 2021	Clarification of language for secondary outcomes analysis criteria
21 January 2022	• Change time between baseline visit (#1) and surgical visit (#2) from 1-2 weeks to within 1 month (+/- 3 days).
23 March 2022	
 
Clarification of post-op DPOAE timing from within 4-8 hours to within 8 hours.
 
Clarification of baseline visit timing to within 30 days (+3 days).
 
Update timing of pre- and post-op dosing.
 
Correct efficacy analysis timing.
 
Addition of audiometry language in situations of an absence of a threshold.
 

04 October 2022	
 
WIN conducted once rather than 3 times.
 
ECG removed from study calendar and pre-op data collection as it is not standard of care
 

18 November 2022 03 March 2023	
 
Update audiometric inclusion criteria
 
Correct air-bone gap inclusion criteria
 
Minor edits for consistency with previous modifications
 

#### 1.0 BACKGROUND AND SIGNIFICANCE

## 1.1 Noise-induced hearing loss (NIHL)

Noise-induced hearing loss (NIHL) is a serious problem. When a service member leaves the military, hearing loss can impact his or her quality of life and employability (Pfannenstiel, 2014). Service members are vulnerable to two types of NIHL: occupational NIHL due to continuous or intermittent noise exposure and acoustic trauma due to a sudden burst of sound. Because no form of hearing protection offers complete protection against noise of that intensity, repeated firing of weapons even with ear protection devices can subsequently lead to occupational NIHL (Chen and Brueck, 2011). Almost every member of the armed forces will be exposed to hazardous noise at some point in his or her career (McIlwain et al., 2008; Kirchner et al., 2012; Yankaskas, 2013), highlighting the urgent need for pharmaceutical intervention. Despite positive outcomes in preclinical studies, to date, no drugs have been approved by the U.S. Food and Drug Administration (FDA) for use in the amelioration of NIHL (Le Prell and Bao, 2012; Mukherjea et al., 2015).

## 1.2 NIHL and its Pathogenesis

After noise exposure, two phases of hearing loss can be measured. The first is a temporary threshold shift (TTS), which is greatest immediately after noise exposure, and gradually lessens within the first 24 hours. The second phase is a permanent threshold shift (PTS), which is measured two to three weeks after noise exposure (for recent review, Ryan et al., 2016; Liberman, 2016). These changes are typically monitored using behavioral pure-tone thresholds, distortion product otoacoustic emissions (DPOAE), or the auditory brainstem response (ABR) to generate an audiogram (a plot of threshold as a function of test frequency). The noise-induced damage is dependent on the noise pattern, intensity, and duration, with longer and louder noises being more hazardous than shorter or quieter sound exposures (Wang et al., 2002; Harding and Bohne, 2007; Chen et al., 2015). In addition, NIHL susceptibility differs markedly among individuals, resulting from the interaction of genetic and environmental factors (Clifford et al., 2016; Groth et al., 2016; Lavinsky et al., 2016). For example, in animals, the C57BL/6J mouse strain is more susceptible to noise than other mouse strains (Davis et al., 2001). In humans, individuals with specific single nucleotide polymorphisms (SNPs) in genes for certain antioxidant enzymes may be more susceptible to NIHL (Lin et al., 2009).

NIHL is caused by sensorineural damage, primarily to the sensory hair cells and primary auditory neurons of the cochlea (Liberman, 2017). Outer hair cells (OHCs) are particularly sensitive to noise. When OHCs are damaged, hearing thresholds increase due to a loss in amplification of the cochlear signal. Recently, Kujawa and Liberman (2006, 2009) have expanded on these classic findings with the observation that certain noise exposures at "benign" levels to rodents can result in

only TTS, but no PTS. Nevertheless, the animals show selective synaptic loss between inner hair cells (IHCs) and spiral ganglion neurons (SGNs) with high thresholds, ultimately accelerating hearing loss over time. Because this cochlear synaptopathy does not change the hearing threshold immediately, the term "hidden hearing loss" has been used to label the hidden synaptopathic injury, and this term has also been used to describe corresponding functional deficits that are assumed to be hidden behind the normal hearing threshold.

Clinically, difficulties with understanding speech in noise have long been observed in older adults with normal audiometric thresholds (e.g. Frisina and Frisina, 1997). Loss of fidelity in the encoding of suprathreshold signals may provide one explanation for this deficit (Sergeyenko et al., 2013; Tremblay et al., 2015). Thus, there is the potential for profound functional consequences after a so-called benign noise exposure that led to only TTS. Of particular concern for military personnel with the potential for repeat exposure (Davis, 2016; Bramhall et al., 2017), further studies have found that benign noise exposures resulting in only TTS can also contribute to PTS after repeated exposure (Wang and Ren, 2012), underpinning the importance of developing pharmaceutical interventions to prevent noise-induced cochlear synaptopathy for military service members.

## 1.3 Molecular Pathways Underlying NIHL

Although mechanical destruction and decreased blood flow contribute to NIHL (Quirk et al., 1991; Mulroy et al., 1998), several key molecular mechanisms such as signaling mediated by an ATP receptor have been identified to contribute to TTS (for recent review, see Kurabi et al., 2017). Common mechanisms underlying both TTS and PTS have also been identified. One is the increase of mitochondrial free radical formation such as reactive oxygen species (ROS) due to noise-induced intense metabolic activity in the cochlea (e.g., Yamane et al., 1995; Ohlemiller et al., 1999; Ohinata et al., 2000; Henderson et al., 2006; Campbell et al., 2007; Darrat et al., 2007). Thus, it is not surprising that attempts to prevent NIHL with antioxidant agents have become the focus of much research in this field (Seidman et al., 1993; Hight et al., 2003; McFadden et al., 2005; Yamashita et al., 2005; for review, see Le Prell and Lobarinas, 2015). However, most of these interventions have been only partially effective or ineffective in preventing NIHL (Lynch and Kil, 2005; Campbell et al., 2007; Kopke et al., 2007; Le Prell et al., 2007). The largely disappointing outcomes may be due to a narrow therapeutic window. As ROS signaling is also important for normal cellular function (for recent review, Sbodio et al., 2018), high doses of antioxidants may have less therapeutic benefit (for example, Kil et al., 2017). Recently, new signaling pathways underlying NIHL have been identified, including deregulation of calcium homeostasis (Guitton et al., 2004; Zine and Van De Water, 2004; Chen et al., 2012; Han et al., 2015; Chen et al., 2015). Deregulation of calcium signaling may contribute to development of both TTS and PTS. In addition, calcium signaling is upstream of many other cellular survival signaling pathways. For example, it can control ROS signaling by regulating the release of ROS from the mitochondrion (Estergerg et al., 2013,

2014). Calcium homeostasis in the cochlea can be regulated by several types of calcium channels, which include voltage-gated calcium channels (VGCCs) (Rodrigues Contreraz and Yamoah, 2001; Adamson et al., 2002; Fuchs, 2002; Schnee and Ricci, 2003). VGCCs can be divided into two groups: high-voltageactivated calcium channels and low-voltage-activated calcium channels (Igelmund et al., 1996; Lacinova et al., 2000; Perez-Reyes, 2003; Yunker and McEnery, 2003). The family of low-voltage-activated, or T-type, calcium channels (Cav3) is composed of three members (Cav3.1, Cav3.2, and Cav3.3) based on their respective main pore-forming alpha subunits: α 1G, α 1H, and α1I (Perez-Reyes, 2003; Yunker and McEnery, 2003). Our studies on drug repurposing have shown that a family of antiepileptic drugs blocking T-type calcium channels can prevent and treat NIHL (Shen et al., 2007; Bao et al., 2013). We have also determined the expression pattern of these calcium channels in the cochlea. All subtypes are present in SGNs, and  $\alpha$  1G and  $\alpha$  1I are expressed in the hair cells and supporting cells (Shen et al., 2007). Thus, it is not surprising that an antiepileptic drug (AED), zonisamide (ZNS), which blocks T-type calcium channels, has both prophylactic and therapeutic functions against NIHL (Bao et al., 2013). In addition, epidemiological studies show that ZNS is well-tolerated even for long-term treatment (Hashimoto et al., 1994; Leppik, 2006, White et al., 2010). These findings have led us to this project, which is the repurposing ZNS against NIHL for military service members.

## 1.4 NIHL and Pharmacogenetics

Preliminary results. Pharmacogenetics (PGx) is the study of how a person's genetic makeup determines his or her response to a therapeutic intervention. It offers the promise of utilizing genetic fingerprints to predict an individual's responses to drugs in terms of safety, efficacy, and pharmacokinetics. It can revolutionize the practice of medicine by individualizing treatment through the use of novel diagnostic tools. To date over 100 loci have been associated with syndromic and non-syndromic hearing loss providing excellent biomarkers for PGx studies. These markers are easily surveyed through both SNP-based or whole exome sequencing using DNA samples taken from patients (Pawelczyk et al. 2009; Konings et al. 2009; Grondin et al. 2015). In a recent study, a genetic risk score for the likelihood of NIHL was developed based on SNP markers in 10 genes (Zhang et al. 2019). Thus, we will test the applicability of this index to predicting both TTS and PTS in patients undergoing skull-base surgery. In addition to examining associations of candidate genes for NIHL, we will also screen patients for known genetic variation associated with the metabolism of ZNS (Saruwatari et al. 2010). Ultimately, we envision incorporating SNPs associated with high risk for NIHL with drug metabolism SNPs to develop predictive models for drug efficacy. These data would be used in dialogue with FDA and subsequent studies to develop personalized drug treatment regimens for patients.

Here, we provide three types of data from our PGx study of age-related hearing loss (ARHL). They are highly pertinent because the same approaches will be applied to this project. First, we describe our recent clinical findings on the delay of ARHL in human subjects taking calcium channel blockers (CCBs). Second, we present our preliminary human genetic studies of ARHL in the same population based on the continuous extreme phenotypes (CEP) and sequence kernel association test (SKAT) approaches. Third, we present an estimate of patient populations using the CEP-SKAT method.

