## 5.5 Follow-Up Assessments

The follow-up assessments will occur after surgery and include the following tests or procedures:

- 1. DPOAE testing in recovery, within 8 hours after surgery.
- 2. Blood samples taken within 12 hours following the first pill for PGx surveys.
- 3. Collection of laboratory test results for research purposes that include an electrolyte panel, BUN, Cr, ALT, and AST. If these tests are not performed as part of clinical care post-operatively, we will obtain them for research purposes at the time of the PGx blood draw.
- 4. DPOAE, Audiogram, ECochG, and WIN testing 30 days (+/-3 days) after surgery.
- 5. Completion of the Hearing History and Occupation Exposure questionnaire 30 days (+/- 3 days) after surgery.
- 6. Documentation of adverse events.

Follow-up assessments will be planned at the stated time points; actual follow up times may vary due to patient logistics and compliance.

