#### 5.6 Blood collection, transportation, and storage

Blood samples will be collected from each participant during the baseline visit and the post-surgery visit within 12 hours after the pre-operative drug dose. A post-operative nurse will draw blood into a red-top tube (EDTA or citrate) using an IV line. Samples will be labeled with a study identification number. They will be stored in a 2-8°C degree refrigerator at WUSM. Samples will then be transported weekly by a study team member for extraction and stored in a -80°C freezer at Gateway Biotechnology's lab.

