#### 12.5 Pharmacogenetics analysis plan

This analysis will be performed at the end of the trial by Gateway Biotechnology. To identify genetic variants with ZNS protection against hearing loss, we will first use univariate logistic regression analyses to identify potential confounding variables: sex, age, Z-scores of drug concentration, Z-scores of noise intensity and duration, and Z-scores of hearing functions measure immediately following surgery. Single-marker allelic association analyses will be conducted on the two imputed data sets in PLINK v1.07. The data will be analyzed with a logistic regression model on the additive continuous dosage of minor alleles from 0 to 2 to account for uncertainty of imputation. We will combine association results in the two cohorts by performing a genome-wide inverse-variance weighting metaanalysis using PLINK v1.07, and assuming a fixed-effect model. Functional annotation of top-associated markers will be performed with R package NCBI2R 1.4.6 (http://CRAN.Rproject. org/package=NCBI2R), and key regional association plots of meta-analyzed results will be generated. To confirm whether these variants are specific to ZNS response, we will apply CEP SKAT to analyze genetic associations based on Z-scores of audiogram average threshold shifts and DPOAE amplitudes. All genetic variants, including both common and rare variants, will be included in this association study. Age, gender, and noise duration and intensity will be adjusted for the analysis. The analysis will also be performed using hearing data collected two weeks following surgery. The only differences will be a) using the Z scores of ECochG AP amplitude, latency, and width as well as WIN score, and b) using average audiogram threshold shifts and DPOAE amplitudes at 30 days post-treatment. We will also include metabolite profiling data to support potential genotypic responses to drug treatments. To control for confounding effects, these models will be adjusted for age, gender, and noise duration and intensity. Finally, the control and ZNS-treated comparisons will be performed using post-hoc comparisons with a Bonferroni adjustment for multiple comparisons of any ZNS versus none. Statistical analyses will be performed using the CEP-SKAT method in R language, and the statistical software SAS version 9.4 for Windows will be used for additional analysis.

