7.1.3 Pharmacogenetics analysis plan

This analysis will be performed at the end of the trial by Gateway Biotechnology. To identify genetic variants associated with ZNS protection against hearing loss, we will utilize genetic and metabolic data collected from patients in a genetic association study. Variables including sex, age, normalized values (Z-scores) of drug plasma concentration, Z-scores of noise intensity and duration, and Z-scores of hearing functions measured immediately following surgery will be included in the analysis of variance. Single-marker allelic association analyses will be conducted on the two imputed data sets using PLINK v1.07. The data will be analyzed with a logistic regression model on the additive continuous dosage of minor alleles from 0 to 2 to account for uncertainty of imputation. We will combine association results in the two cohorts by performing

a genome-wide inverse-variance weighting meta-analysis using PLINK v1.07, and assuming a fixed-effect model. Functional annotation of top-associated markers will be performed with R package NCBI2R 1.4.6 (http://CRAN.Rproject. org/package=NCBI2R), and key regional association plots of meta-analyzed results will be generated. To confirm whether these variants are specific to ZNS response, we will apply CEP SKAT to analyze genetic associations based on Z-scores of audiogram average threshold shifts and DPOAE amplitudes. All genetic variants, including both common and rare variants, will be included in this association study. Age, gender, drug concentration, and noise duration and intensity will be adjusted for the analysis. The analysis will also be performed using hearing data collected two weeks following surgery. The only differences will be a) using the Z scores of ECochG AP amplitude, latency, and width as well as WIN score, and b) using average audiogram threshold shifts and DPOAE amplitudes at 30 days (+/- 3 days) post-treatment. We will also include metabolite profiling data to support potential genotypic responses to drug treatments. To control for confounding effects, these models will be adjusted for age, gender, and noise duration and intensity. Finally, the control and ZNS-treated comparisons will be performed using post-hoc comparisons with a Bonferroni adjustment for multiple comparison testing. Statistical analyses will be performed using the CEP-SKAT method in R language, and the statistical software SAS version 9.4 for Windows will be used for additional analysis.

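### The genetic plan names an extreme-phenotype method (CEP-SKAT) for a cohort not selected on phenotype, with no tail cut-off or analysis set; ordinary SKAT or SKAT-O on everyone genotyped would keep all the information

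*Protocol*

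**What the plan says.** **The method.** Protocol 1.4 reports preliminary work in a different condition, age-related hearing loss, "based on the continuous extreme phenotypes (CEP) and sequence kernel association test (SKAT) approaches". It presents those data as relevant to this trial: "They are highly pertinent because the same approaches will be applied to this project".

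The operative text is Protocol 12.5, repeated almost unchanged in SAP 7.1.3. It starts with a conventional step: "Single-marker allelic association analyses will be conducted on the two imputed data sets in PLINK v1.07", using logistic regression on allele dosage. To check whether the variants found are specific to zonisamide response, it then says "we will apply CEP SKAT to analyze genetic associations based on Z-scores of audiogram average threshold shifts and DPOAE amplitudes". Common and rare variants are both included. A further run brings in ECochG and WIN scores. The section closes with "Statistical analyses will be performed using the CEP-SKAT method in R language".

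**The participants.** Protocol 5.6 says "Blood samples will be collected from each participant during the baseline visit". Protocol 5.5 schedules "DPOAE, Audiogram, ECochG, and WIN testing 30 days (+/-3 days) after surgery", and the calendar in Protocol 9.0 shows the same tests at baseline. Protocol 12.3 sets total enrolment at 234, that is 78 per arm.

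**What is absent.** Neither document gives a tail fraction or cut-off, a rule for selecting extreme participants, a reason for using extremes, or the analysis set for the CEP-SKAT step.

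**The concern.** An extreme-phenotype design pays off when many people have been phenotyped but only some can be genotyped. Choosing the tails then gets more information from a fixed number of assays. Nothing in these documents describes that situation. Recruitment does not depend on hearing outcome, blood is taken from everyone, and the hearing tests are scheduled for everyone.

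If DNA from all participants is assayed, an analysis restricted to the tails can at best match an analysis of everyone, and usually loses something. How much it loses depends on a cut-off that the plan leaves open, so the choice could be made after the data are seen.

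At stake is efficiency and clarity in a genetic analysis that is already small. Protocol 2.2 lists this work as a secondary objective; SAP 2.2.3 calls it exploratory.

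**Working it through.** **The plan's own figure.** The documents state no power or sample size for the genetic analysis. The only power figure is 80.4% for the primary endpoint (Fisher's exact test, 50% v 25%, 78 per arm, one-sided 0.0125). It reproduces, at 80.4% by the arcsine approximation and 80.7% by full enumeration, but it has no bearing on this point.

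**Inputs.** N = 234 is from Protocol 12.3 and is an upper bound. The fraction *t* in each tail is not in the documents, so a range of 10% to 33% is assumed. The trait is assumed normal with unit variance, with one additive variant and no covariates.

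**Formula.** Suppose only participants beyond ±c are analysed, where c is the normal quantile at 1 − t, and the likelihood allows correctly for that selection. The information on a small genetic effect, relative to using everyone, is the part of the trait variance that lies in the tails:

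ratio = 2[c·φ(c) + t]

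| Each tail t | c | φ(c) | Ratio | Kept of 234 | Left out | Equivalent N |
|---|---|---|---|---|---|---|
| 10% | 1.282 | 0.1755 | 2(0.2249 + 0.1000) = 0.650 | 47 | 187 | 152 |
| 20% | 0.842 | 0.2800 | 2(0.2356 + 0.2000) = 0.871 | 94 | 140 | 204 |
| 25% | 0.674 | 0.3178 | 2(0.2143 + 0.2500) = 0.929 | 117 | 117 | 217 |
| 33% | 0.431 | 0.3636 | 2(0.1566 + 0.3333) = 0.980 | 156 | 78 | 229 |

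The loss therefore runs from about 2% to 35%. It is smaller than the head-count suggests because values near the mean carry little information.

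**Illustration in power terms (single variant, not a SKAT set test).** Assume a variant that explains 5% of trait variance, tested two-sided at 0.05/8 (critical value 2.73). Power = P(Z > 2.73 − √(234 × ratio × 0.05/0.95)).

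- Everyone: √12.32 = 3.51, power 78%.
- 10% tails: √8.00 = 2.83, power 54%.
- 20% tails: √10.73 = 3.28, power 71%.
- 25% tails: √11.44 = 3.38, power 74%.

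**Check by simulation.** 20,000 data sets were generated under different assumptions (allele frequency 0.20, 3% of variance, two-sided 0.05) and analysed by ordinary linear regression. At N = 234, power was about 76% with everyone and 55%, 69% and 72% with 10%, 20% and 25% tails. At N = 156 (the two zonisamide arms only), it was about 58% against 39%, 52% and 55%. With no genetic effect, the tail analyses rejected in 4.8% to 5.1% of data sets, so false positives were not inflated in this setting.

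**The case against.** A reader might infer that the plan must either throw away the middle of the cohort or fit a wrong, truncated likelihood to everyone. The documents do not support that. They expand the abbreviation and say no more: no cut-off is set, no mid-range participant is excluded, and no likelihood is written down. The traits are described as continuous Z-scores. A third reading is open, in which no cut-offs are applied and the method reduces to ordinary continuous-trait SKAT on everyone. This objection stands against the either/or. It does not rescue the text, because that third reading is the analysis recommended here and the plan does not state it.

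Other limits also stand:

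- **Scope.** The whole genetic analysis does not rest on extremes. The PLINK single-marker analysis comes first and is not described as extreme-phenotype based.
- **The calculation.** The figures above concern one assumed variant. No SKAT set-test power was computed.
- **Genotyping.** Collecting blood from everyone is not the same as assaying everyone. Protocol 1.4 mentions both SNP-based and whole exome approaches, and the documents do not rule out sequencing a subset. If that were intended, choosing extremes could save assay cost, but the plan would need to say so.
- **Sample size.** The note in Protocol 3.2 removes some participants from the DPOAE, ECochG and WIN analyses. An analysis of zonisamide response might also concern only the 156 treated patients. So 234 is a ceiling.
- **Size.** With wide tails the loss is slight.

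**Conclusion.** The point holds as a method choice to correct. CEP-SKAT is named for the step after the single-marker analysis in a cohort that is not selected on phenotype, with neither cut-offs nor an analysis set. Applied as its name implies, it would keep about 65% of the information with 10% tails and 98% with outer thirds, and nothing in the documents offsets the loss. These figures assume a normal trait, a single variant, no covariates and genotyping of all samples; the tail fractions are an assumed range.

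The documents do not show that data will be discarded, that a wrong likelihood will be fitted or that false positives will rise. The primary analysis is not touched. This is a low-priority improvement to work that the SAP calls exploratory.

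**What to change.** In Protocol 12.5 and SAP 7.1.3:

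1. Replace CEP-SKAT, at both mentions in each section, by ordinary SKAT or SKAT-O on the continuous phenotype, with no selection on outcome.
2. State the analysis set: all genotyped participants with that phenotype measured. This is at most 234, and fewer for DPOAE, ECochG and WIN after the exclusions noted in Protocol 3.2. Say whether the zonisamide-response step uses all arms or the treated arms only.
3. If an extreme-phenotype run is kept, label it descriptive and fix its cut-offs before the outcome data are seen.
4. If only a subset is to be sequenced, say so and give the selection rule and the reason.

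The cost is wording and a little analysis work, with no new visits or blood draws. This assumes that the samples already collected are genotyped for everyone; if they are not, items 1 and 2 would add assay cost.
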